4.0 Research Design and Methods

4.1 Type of Study

This is a single-site study that will take place at VA Pittsburgh Healthcare System, Pittsburgh, PA. It is a prospective randomized clinical trial evaluating the two different nerve block injection drugs for TKA and THA, introduced above and described further below. All described RegA techniques strategically avoid GETA and high-dose opioids, and the immediate postoperative complications (from GETA and high-dose opioids) that inhibit full-capacity cognitive function needed to accomplish PT/OT goals during the first 2 days after TKA/THA. Two hundred (200) total patients will be recruited and evaluated for study outcomes pre-TKA/THA (100 for TKA, 100 for THA). Following pre-surgical evaluation, patients will be block-randomized (stratified by [a] TKA vs. THA surgical procedure, [b] age, and [c] presence of diabetes). After surgery, all patients will undergo the same standardized PT/OT best-evidence care plans consistent with current clinical care at our institution. Evaluation of study outcomes will take place during the first two days after surgery, throughout the remainder of the hospital stay (which typically ranges from 2 to 5 days, including discharge day), and during the first two orthopedic post-op follow-up evaluations. The primary outcome is pain at 24 hr after surgery, and exploratory outcomes include physical therapy progress and anesthesia-related symptoms. We will also assess additional metrics of anesthesia and physical therapy success such as range of motion, physical function and performance testing, length of hospital stay, discharge placement, readmission, falls, and other adverse events.

Study Treatment Groups:

Institutional Standard of Care (ISOC)

All patients will receive a standardized bupivacaine spinal anesthetic, consistent with current institutional practice. All patients will receive pre-medications for the prevention of pain, nausea, vomiting, and gastroesophageal reflux, consistent with current institutional practice. All patients will receive intravenous hydration, intravenous antiemetics, and intravenous blood pressure support (e.g., intravenous phenylephrine bolus/infusion) consistent with our current institutional practice. The need for intraoperative blood transfusion will occur based on current institutional practice and collaborative decision-making between the surgical and anesthesia teams, consistent with current institutional practice.

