4.3 Study Visits & Procedures

Study Visits:

The study procedures to be conducted for each subject enrolled in the study are presented in tabular form in Appendix 1 and described in the text that follows. Additional information is provided in the manual of operating procedures.

The study team will attempt to coordinate all of the research questionnaires and physical therapy sessions with the patient's other inpatient and outpatient appointments at VAPHS. However, if this is not possible, the patient will be required to come in for additional visits to complete the research surveys and physical tests at the described study time-points. The total additional time required for the subject participating in this research study is approximately 4-5 hours (not including transportation to and from VAPHS). Patients participation in this study will be approximately 3-4 months and will consist of 1-2

visits prior to surgery, the day of surgery visits (pre- and post- surgery), their in-hospital post-surgery visits and two follow-up visits, scheduled in conjunction with their standard of care ortho scheduled post-surgery visits.

After surgery, all patients will undergo the same standardized PT/OT best-evidence care plans (knee-specific, and hip-specific, respectively) consistent with current clinical care at VA Pittsburgh Healthcare System.

Throughout the study and after the patient signs consent, if the patient is signed up to use the VA MyHealtheVet online tool, communication between the patient and study team can occur using the secure messaging tool offered through MyHealtheVet.

Screening/Baseline Visits

The screening and baseline visit can be completed on the same day, if feasible. No research screening or baseline procedures can be conducted until informed consent is complete.

Baseline assessments will include demographics (including age and weight), smoking status, diabetes status, comorbidity (CIRS: cumulative illness rating scale), completion of research questionnaires, and completion of physical therapy procedures.

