For patient-reported outcome of function, we will use the data generated by Western Ontario and McMaster Universities Osteoarthritis Index Physical Function Subscale (WOMAC-PF). The entire WOMAC instrument will be administered. This instrument was developed based on patient input and is the instrument of choice to assess outcome post-TKA and THA (20). The WOMAC-PF consists of 17 items related to physical function. Each item is scored on a 5-point Likert-type Scale with descriptors from 0-4 (none, mild, moderate, severe, and extreme difficulty). Scores of each item are summed for a maximum total score on the WOMAC-PF of 68. Higher scores indicate worse functional limitations. Reliability and validity of this instrument have been established (25-27). This will be given before surgery and at Follow-Up Visit 2 after surgery. Licensing rights to this questionnaire have been purchased by the study team for use in this research study.

Falls Questionnaire:

Throughout the study, the patients will be asked about their falls history. The information collected will include but is not limited to, how many falls the patient experienced in the past year (done at baseline), how many falls since the last assessment (in-hospital visits and Follow-Up Visit 2), questions regarding loss of balance, whether or not the patient is afraid of falling, and was medical treatment sought after any falls.

Clinical Assessments

None of the clinical assessments listed below are being done due to safety concerns, as such, if the physical therapist or treating physician feels that due to the patients' medical condition (such as a knee immobilizer), that some or all of the physical therapy tests cannot be completed at the specified protocol time points; the physical therapy testing will be considered optional for these patients and will be done at the discretion of the treating physician and physical therapist. If physical therapy testing is not completed due to the patient preparing for discharge and/or the patient has been discharged, this will not be considered a protocol deviation.

Gait Speed: Self-selected gait speed is measured in meters/second while subjects walk a 4 meter path located in the middle of a longer path of 9 meters to avoid acceleration or deceleration. Subjects are asked to walk at their regular pace, and time is measured with a stop watch. This test takes around 2 minutes.

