APPENDIX 1: Study Calendar

	Screening Visit ^a	Baseline Visit	Day of surgery		Post-Op Day 1	Post-Op Day 2	Post-Op Day 3	Post-Op Day 4	Post-Op Day 5	Follow-Up Visit 1 ^d	Follow-Up Visit 2 ^{c, e}
			Pre-Procedure	Post-Procedure							
Clinical Assessments											
Informed Consent	X										
Determine Eligibility	X										
Demographics	X										
Orthopedic & IMPACT evaluation		X									
Crude Sensation in L2-L4 & L4-S3		X			X	X	X	X	X		X
Straight Leg Raise & Range of Motion		X			X	X	X	X	X		X
Functional Independent Measure (FIM)		X			X	X	X	X	X		X
Standing Balance Test		X			X	X	X	X	X		X
Single Leg Balance Test ^g		X									X
Gait Speed		X			X	X	X	X	X		X
Repeated Chair Stand Test		X				X	X	X	X		X
Stair Climbing Time		X									X
Physical Therapy/ Therapeutic Exercises					X	X	X	X	X		
Comorbidity (CIRS)		X									
Interim Changes											X
Discharge Disposition											X
Opioid Consumption					X ^g						
Anesthesia/Study Drugs			X								
Adverse Events		X	X	X	X	X					
Concomitant Medications		X	X	X	X	X					

	Screening Visit	Baseline Visit	Day of surgery		Post-Op Day 1	Post-Op Day 2	Post-Op Day 3	Post-Op Day 4	Post-Op Day 5	Follow-Up Visit 1	Follow-Up Visit 2 ^{c, e}
			Pre-Procedure	Post-procedure							
Questionnaires											
SFMPQ-2 ^b		X	X	X	X	X	X	X	X		X
DVPRS		X	X	X						X	X
DVPRS- in hospital ^b					X	X	X	X	X		
ORSDS ^b		X			X	X	X	X	X		
QOR-15 ^b		X			X	X	X	X	X		X
WOMAC		X									X
SF-8 ^b			X		X	X	X	X	X	X	
SF-36		X									X
Falls Questionnaire		X			X	X	X	X	X		X

a. The screening visit and baseline visit can be completed on the same day.

b. On post-op hospital days and post-op week 6 follow-up visits, these questionnaires will be completed before the subject has their first physical therapy session for the day.

c. If a patient decides to withdraw from the study after having their surgery, or is withdrawn by the study team during or after their surgery, they will be asked to complete Follow-Up Visit 2.

d. Follow-up visit 1 will occur with the patient's already scheduled standard of care follow-up orthopedic visits. Follow-Up Visit 1 may be performed as a phone call if necessary.

e. Follow up visit 2 will be scheduled to coincide with the patient's standard of care follow-up orthopedic visits.

f. Patient must pass the standing balance test first, before the single leg balance test can be attempted.

g. Opioid consumption will stop being collected at the time of the patient's discharge.

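### The first in-hospital falls form can pick up falls from before surgery, because its recall window starts at the previous falls assessment and that is the Baseline Visit

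*Combined protocol and SAP*

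**What the plan says.** Section 4.1 lists falls among the additional metrics to be assessed: "length of hospital stay, discharge placement, readmission, falls, and other adverse events".

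Section 4.3, under Falls Questionnaire, gives two recall periods. At baseline the patient reports "how many falls the patient experienced in the past year (done at baseline"). At later visits the item is "how many falls since the last assessment (in-hospital visits and Follow-Up Visit 2"). The paragraph introduces its content as a list that is not exhaustive. It mentions neither a date for each fall nor a start point tied to surgery or to the block.

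In Appendix 1 the row reads "Falls Questionnaire X X X X X X X". Set against the 11 visit columns, the seven marks fall at Baseline, Post-Op Days 1 to 5, and Follow-Up Visit 2. Screening, both day-of-surgery columns and Follow-Up Visit 1 are blank.

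The baseline assessment is separate from the day of surgery. Section 4.3 counts "visits prior to surgery, the day of surgery visits (pre- and post- surgery") as distinct contacts and fixes no interval between them. A repeat baseline visit is possible after a significant change in health, but section 4.3 expects it only rarely and lets the patient decline.

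**The concern.** A falls count taken on the first day after a nerve block would naturally be read as falls after the block. Under the stated recall rule it is not that. It also takes in any fall at home between the baseline visit and the operation, and nothing in the described item lets the analyst separate the two.

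The count nearest the block is also the one of most interest for safety. Section 2.1 expects numbness to bring loss of muscle strength. Section 7.3 says it is not known by formal study whether the four-drug block gives longer unwanted numbness than plain bupivacaine. Early falls bear on that question, so an early count made up partly of preoperative events describes it poorly.

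**Working it through.** The documents state no figure for this point, so there is none to reproduce. The check sets the wording against the schedule and then asks how much of the window lies before surgery.

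**Step 1: where each window starts.**

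| Falls form | Previous falls form | Window |
|---|---|---|
| Baseline | none | past year |
| Post-Op Day 1 | Baseline | wait for surgery plus about 1 day after the block |
| Post-Op Days 2-5 | the day before | about 1 day, all after surgery |
| Follow-Up Visit 2 | last in-hospital form | all after surgery |

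Only the first in-hospital form crosses the date of surgery. If Post-Op Day 1 is missed, the problem moves to the next form completed.

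**Step 2: share of the Post-Op Day 1 window before surgery.** Let D be the days from baseline to surgery, with about 1 day from block to form. The share is D/(D+1). D is not in the documents, so a range is shown:

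- D = 1: 1/2 = 50%
- D = 7: 7/8 = 87.5%
- D = 14: 14/15 = 93%
- D = 30: 30/31 = 97%

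A rough upper guide to D comes from two statements: "Patients participation in this study will be approximately 3-4 months", and a footnote to Appendix 1 that still speaks of "On post-op hospital days and post-op week 6 follow-up visits". With 30.44 days per month, 3 × 30.44 − 42 = 49 days and 4 × 30.44 − 42 = 80 days, or 98% and 99% of the window. Both inputs are approximate. The rationale for Amendment 6 in Appendix 2 notes that follow-up visits do not always fall at the nominal weeks.

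**Step 3: effect on the comparison.** Let a and b be the true early fall rates per patient in the four-drug and control arms, and c the preoperative falls per patient that enter the form. These falls precede the block, so randomization gives the same expected c in both arms.

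- Difference: (a + c) − (b + c) = a − b, unchanged in expectation.
- Ratio: (a + c)/(b + c), closer to 1 than a/b whenever c > 0.
- Variance of the difference, treating counts as Poisson with 160 and 40 patients (section 4.1): it rises by c × (1/160 + 1/40) = 0.03125c.

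**Step 4: illustration only.** No fall rate is in the documents. Assume a = 0.03 and b = 0.01 (true ratio 3.0), and 0.25 to 1.0 preoperative falls per patient-year, so c = rate × weeks/52.

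| Wait | c | Preoperative falls in 200 patients | Ratio observed |
|---|---|---|---|
| 1 week | 0.005 to 0.019 | 1.0 to 3.8 | 2.35 to 1.68 |
| 7 weeks | 0.034 to 0.135 | 6.7 to 26.9 | 1.46 to 1.14 |
| 11 weeks | 0.053 to 0.212 | 10.6 to 42.3 | 1.32 to 1.09 |

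Under the same assumptions the standard error of the difference is √(0.03/160 + 0.01/40) = 0.021 without contamination. It becomes 0.024 at the mildest corner of the table and 0.084 at the most severe.

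**The case against.** Several points on the other side carry weight.

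- **The adverse-event record may already date some falls.** Section 4.1 groups falls with other adverse events. Appendix 1 marks adverse events separately at Baseline, Pre-Procedure, Post-Procedure and Post-Op Days 1 and 2, and section 5.2 plans product-limit estimates, which need event times. This stands: a reader should not infer that no other record could separate falls before and after the block. But nothing links that record to the questionnaire count or uses it to reclassify a reported fall.
- **No tabulation rule exists.** A reader might infer that preoperative falls will be reported as in-hospital falls. Section 5 defines no in-hospital falls variable, so the documents support only that they can enter the count.
- **The form itself is not in the documents.** Section 4.3 summarises it and refers to a manual of procedures for more detail. A date field or a surgical anchor could exist. It cannot be assumed, and the protocol sentence would still need to match it.
- **The recall phrase could mean any study contact.** Section 4.3 uses the word assessment more broadly for the DVPRS, which Appendix 1 also schedules on the day of surgery. That reading would start the window on that day. It is possible but less natural inside the Falls Questionnaire paragraph, and two available readings would themselves give inconsistent answers.
- **A hidden harm signal is too strong an inference.** The expected difference between arms is unbiased. If true in-hospital falls were 1-3% (an assumption), the 40 controls would have 0.4 to 1.2, so a comparison between arms would say little even with perfect wording.

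**Conclusion.** The point holds in a limited form. The stated recall period and the stated schedule together make the first in-hospital falls count span the preoperative wait, so falls before surgery can be included in it. Later in-hospital forms, Follow-Up Visit 2 and the primary outcome are not affected.

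The consequence is an inflated absolute early fall rate in both arms, a noisier comparison, and a ratio drawn towards 1. It is not a systematic bias in the difference between arms, and the documents do not show that a harm would be concealed.

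The number of misplaced falls cannot be derived, because it depends on a wait and a fall rate that the documents do not give; the counts and ratios in the working are illustrations. What does not depend on a fall rate is the makeup of the window: if the wait is a week or more, at least 87.5% of the Post-Op Day 1 window precedes surgery. The conclusion assumes that the recall phrase refers to the previous falls assessment and that the form carries no date or surgical anchor beyond what section 4.3 describes.

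**What to change.** On the first in-hospital falls form, normally Post-Op Day 1, ask for falls since the surgery or nerve block. Keep the current recall period for later forms, and record the date of each fall. Change the sentence in section 4.3 to match. If falls between baseline and surgery are wanted, ask at the existing Pre-Procedure contact, where other questionnaires are already given, and treat the answers as baseline history.

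For patients already enrolled, classify falls on the first form as before or after the block from chart or adverse-event dates where these exist. Some falls at home before surgery may not be recoverable, which favours making the change early.

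The cost is a small form revision and one protocol sentence, with no new visit. The drawback is two versions of the first in-hospital item across the trial, so the version used should be kept in the data set.

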“Nerve block analgesia” is not necessarily synonymous with “nerve block numbness.” Analgesia is “pain relief,” and pain relief without numbness is thought to promote early physical therapy. Nerve block numbness (even though the numbness is indeed providing pain relief) is expected to delay physical therapy due to lack of muscle strength during numbness. One of the goals of the study’s exploratory aims is to determine if the MMPNA 4-drug combination provides both improved pain relief and improved physical therapy in the days after surgery (when compared with plain bupivacaine).

Anesthesia planning for invasive orthopedic surgery after battlefield-sustained polytrauma above and below the abdomen typically requires general endotracheal anesthesia (GETA) for surgical stabilization of all traumatic injuries. However, based on recent anesthetic innovations, GETA is no longer required for elective TKA/THA, and therefore GETA is not specifically required for one-sided lower-extremity polytrauma. For TKA/THA, the exclusive use of RegA (without GETA) is not only feasible and sufficient, but also comparatively effective via reductions in morbidity and mortality (based on population data).⁽²⁾ GETA has temporary adverse effects on immediate postoperative cognitive function after surgery, and the cognitive risks after multiple episodes of GETA is unknown but is unlikely to be beneficial long term. Eliminating GETA as a confounder of immediate physical therapy / occupational therapy (PT/OT) outcome evaluation now allows for proper evaluation of anesthesiologist physician-directed pain relief, and this study of veteran-specific care has the potential to immediately translate to the care of injured military personnel.

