Repeated Chair Stand Test: The repeated chair stand test is a simple test to assess strength of the muscles of the lower extremities and static balance. It measures the time that a person takes to stand from a chair 5 times. It takes approximately 1 minute to complete the repeated chair stand test.

Standing Balance Test:

This test is only performed on those patients who can stand unassisted without the use of a cane or walker. Moreover, the participant stands at an arm's reach of a steady surface on one side (*e.g., bed head/sideboard, grab bar*) and the tester on the other side. There are three (3) balance tests that differ by their feet position (*i.e., side-to-side, semi-tandem, and tandem*). The balance tests are performed at each assessment visit. For each:

1. The tester will ask the participant if they can stand without the device and are willing to try the test. If they reply “yes” the tester can assist them with getting into the correct position for testing.
2. The tester, for each position, will not only describe to the participant what the test is but will also demonstrate the appropriate position of the feet for testing.
3. The participant will get into the proper position while receiving support from the tester.

When the participant appears to be steady, ask if they are ready. When they reply “yes”, the tester says “Ready, begin”. The tester begins timing (i.e. starts the stopwatch) once the participant is standing independently without support from the tester. The timing for each test continues until the participant moves their feet, grabs for support, receives support from the tester or the time (10 seconds) has elapsed. This exam takes around 3 minutes.

Single Leg Balance Test:

This test will only be performed in patients who were able to complete the standing balance test. The single leg balance test is recommended to quickly assess global functional level, and its scores are related to risk for falls.

- Participants are asked to stand on one foot for 45 seconds. The other foot is raised so that the raised foot is near but not touching the ankle of their stance limb.
- The participant may use the arms, bend the knee, or move the body to maintain balance.

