5.0 Statistical Analysis

5.1 Analysis Plan

Data will first be assessed for outliers (+/- 2 SD from the mean) and normality. Outliers will be corrected, if possible, or dropped from the analyses. Distribution, measures of central tendency, variability, and normality will be examined. Data transformations or non-parametric techniques will be applied as needed. We will delete observations with missing values. Spearman correlation coefficients will be computed to examine associations between nerve block drug treatments, replacement surgery

type (hip versus knee), and the outcome measures (SF-MPQ, SF-8, SF- 36, WOMAC, FIM, repeated chair stand test, Opioid Symptom Distress Scale, Defense and Veterans Pain Rating Scale and its Supplemental Questions) from all time points (1 day, 2 day, 3 day, 4 day, Follow-Up Visit 1, Follow-Up Visit 2). Associations between the outcomes across time points will also be examined with Pearson (SF-MPQ, SF-8, SF-36, WOMAC, repeated chair stand test, Opioid Symptom Distress Scale) and Spearman (FIM, Defense and Veterans Pain Rating Scale and its Supplemental Questions) correlation coefficients. We will test all hypotheses and aims by conducting longitudinal multi-level modeling. The level-one unit will be the repeated measures across time, the level-two unit will be the individual patient, and the level-three unit will be nerve block type and surgical site (knee versus hip) groupings (with additional analyses involving age and diabetes status, reflecting the randomization strata). This mixed model procedure will allow the assessment of outcome and exposure variables relationships while adjusting for covariates, and separate assessments of fixed and random effects (i.e., group and individual-level data) using highly correlated repeated measures data. Covariates included in modeling will be age, diabetes status, gender, weight, smoking status, initial health status (e.g., baseline SF-8 / SF-36 and WOMAC), and concurrent general health status (e.g., daily SF-8, subsequent SF-36, and WOMAC).

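### Patients unable to do the timed performance tests get no score and are deleted, which can attenuate or mask an arm difference in either direction

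*Combined protocol and SAP*

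**What the plan says.** Under Clinical Assessments, section 4.3 covers the case where the therapist or treating physician judges that the patient's condition means "some or all of the physical therapy tests cannot be completed at the specified protocol time points". Then "the physical therapy testing will be considered optional for these patients" and is left to their discretion; a knee immobilizer is the example given. A separate sentence deals with discharge: "If physical therapy testing is not completed due to the patient preparing for discharge and/or the patient has been discharged", the omission is not a deviation.

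The balance tests have their own gates. For standing balance: "This test is only performed on those patients who can stand unassisted without the use of a cane or walker". For single leg balance: "This test will only be performed in patients who were able to complete the standing balance test". Section 4.3 gives an untested patient no floor value, no category for inability and no reason code.

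Section 5.1 handles the gaps in one sentence: "We will delete observations with missing values". It names no sensitivity analysis for missing data. The exploratory outcomes then go into mixed models. The section 5.1 outcome list names the repeated chair stand and the Functional Independence Measure (FIM), but not gait speed or balance. Section 4.1 counts performance testing among the measures of success, and section 5.1 commits physical therapy progress to modelling.

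Appendix 1 schedules gait speed and standing balance from post-operative day 1 and the chair stand from day 2. Single leg balance and stair climbing are scheduled only at baseline and Follow-Up Visit 2.

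**The concern.** Sections 1.0 and 2.1 ask whether the longer block gets in the way of rehabilitation. Section 2.1 says that block numbness "is expected to delay physical therapy due to lack of muscle strength during numbness", and section 2.2 expects rebound pain to hold back therapy goals. Either route could leave a patient unable to be tested, so inability is a bad value of the outcome and could follow from the assigned block.

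If such patients have no score and their observations are deleted, the comparison is conditioned on something that happens after randomization. A mixed model on the remaining rows is valid when data are missing at random. It does not repair missingness caused by the unobserved poor performance itself.

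At stake is the rehabilitation conclusion. A finding of no difference on these tests could not be told apart from a difference that deletion had removed. Section 1.0 foresees the results possibly supporting wider adoption of the four-drug block.

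**Working it through.** **Is there a plan figure to reproduce?** No. The power figures in section 5.6 concern block duration. The documents give no effect size, power or expected missing share for any performance test, so the numbers below are illustrations on stated assumptions.

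**Step 1: can treatment-related inability reach the test days?** Section 2.1 puts mean analgesia with the four-drug block at about 36 hours and section 5.6 uses 40 hours. Day 1 and day 2 tests can fall within or close to that period. Section 6.4 requires every participant to walk more than 3 m without a device at entry, so failing the standing gate after surgery reflects a change since enrolment. The Amendment 6 rationale in Appendix 2 reports several instances of therapy assessments not done for medical reasons after 22 patients, so the situation has occurred.

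**Step 2: simplest illustration (gait speed).** Assume that able patients in both arms average 0.6 m/s, with 30% of the four-drug arm and 15% of controls unable.
- Able patients only: 0.6 − 0.6 = 0.
- Inability counted as 0 m/s: (1 − 0.30) × 0.6 − (1 − 0.15) × 0.6 = 0.42 − 0.51 = −0.09 m/s.
- With 20% and 10% unable: 0.48 − 0.54 = −0.06 m/s.
- Swapping the arms changes the sign to +0.09 or +0.06, and the able-only difference is still 0.

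Equal means among able patients are an assumption, and they force the zero. Step 3 drops that assumption.

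**Step 3: truncation model.** Let performance be normal with SD 1, mean 0 in the better arm and −d in the worse arm. Patients below an ability threshold c are not tested. The mean among tested patients is μ + φ(c − μ) / [1 − Φ(c − μ)].

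For d = 0.5 and 10% of the better arm unable, c = −1.282:
- better arm: 0.1755 / 0.90 = 0.195;
- worse arm: 21.7% unable, mean −0.5 + 0.294 / 0.783 = −0.124;
- difference among tested patients: −0.124 − 0.195 = −0.319, which is 64% of the true −0.5.

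| Better arm unable | Worse arm unable | Difference among tested (SD) | Share of truth kept |
|---|---|---|---|
| 5% | 13% | 0.37 | 74% |
| 10% | 22% | 0.32 | 64% |
| 20% | 37% | 0.26 | 51% |
| 30% | 49% | 0.21 | 43% |

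Over the same range the share kept is 77% to 45% for d = 0.3, and 70% to 39% for d = 0.8. The arm labels are interchangeable, so the attenuation is the same whichever arm is worse.

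**Step 4: effect on power.** Simulation with 3000 runs, four-drug arm worse by d = 0.5, two-sided α = 0.05, and 10% or 20% of controls unable:

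| Controls v four-drug | No one untestable (t-test) | After deletion (t-test) | Inability as worst rank (Wilcoxon) |
|---|---|---|---|
| 20 v 80 (one procedure) | 52% or 51% | 34% or 27% | 49% or 48% |
| 40 v 160 (both) | 81% or 81% | 57% or 46% | 78% or 77% |

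The outlier rule in section 5.1, "Outliers will be corrected, if possible, or dropped from the analyses", can also remove very slow patients who were tested. Applied after deletion at d = 0.5, it lowers the difference to about 0.24 SD (10% unable) or 0.19 SD (20% unable).

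**Step 5: discharge.** Tests missed because the patient has left probably remove better performers. That pull is opposite to the one from inability, so the net effect could differ by day. Deletion treats both kinds of gap alike.

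**The case against.** The strongest reply is that inability is not lost altogether. FIM covers transfers, walking and stairs, scores total dependence as 1, is scheduled on days 1 to 5 and is in the section 5.1 outcome list. Straight leg raise is recorded as No when the patient cannot do it. Falls, length of stay and discharge placement are also assessed. This largely stands, and it limits the point to the timed tests. It does not remove it: FIM and straight leg raise sit under the same optional clause, with no floor rule when they are skipped.

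A reader might infer that the plan hides harm from the four-drug block. The documents do not support a one-way bias. Section 3.6 gives both arms the same bupivacaine concentrations. Section 2.2 calls the adjuvants motor sparing, and section 5.2 expects them to prolong analgesia without numbness. On that reasoning the control patients, with earlier rebound pain, could be the ones unable to test, and deletion would then mask a benefit.

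Several narrower objections also stand:
- The general trigger is a medical condition judged by clinicians, so not every skip is block-related.
- The gate on standing unaided applies to standing balance and, through it, single leg balance. Gait speed and chair stand have no such gate.
- Study staff are blinded (section 4.1), so knowledge of the arm should not drive skipping. The patient's physical state still can.
- The manual of procedures and the case report forms are not available here and may hold a reason field. Section 5.1 makes no use of one.

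**Conclusion.** The point holds for the repeated chair stand, gait speed and standing balance. Optional or gated testing followed by deletion leaves a comparison among patients able to perform, and that can attenuate or mask a difference in either direction. Of these three tests, only the chair stand is in the section 5.1 outcome list.

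The size in this trial is unknown. The retained shares of 39% to 77% rest on a normal model, true differences of 0.3 to 0.8 SD and 5% to 30% of the better arm unable. None of these comes from the documents. They show that the loss can be material, not that it will be.

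Two further readings would go too far. The 24-hour SF-MPQ endpoint is a questionnaire outside the physical therapy clause, so the primary result is not affected. Nor would all evidence of impairment disappear, since FIM and straight leg raise record part of it when done. The affected outcomes are exploratory, so this is a correction worth making, not a threat to the main conclusion.

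**What to change.** Replace the blanket deletion rule for these tests; the clinical discretion to skip a test can stay as it is.

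1. Have the blinded testers record one reason for each test not done: unable because of weakness, numbness or pain; other medical reason, such as an immobilizer; discharged or preparing for discharge; other.
2. Report the proportion unable by arm and day, stratified by procedure.
3. Keep the planned mixed model and add a worst-rank analysis that scores inability from weakness, numbness or pain as the worst outcome.
4. Add a sensitivity analysis that also ranks other medical reasons as worst. Making this the main analysis would be debatable, because an immobilizer may have nothing to do with the block.
5. Treat discharge-related misses as missing, not as failure.

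The cost is one data field (possibly already on the forms), a short addition to section 5.1 and a little more analysis. Inability unrelated to the block will add some noise to the worst-rank result.
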